Appropriate members of the women's health care team will serve as data reporters to the registry based on information in the medical record. Only data noted as part of routine care will be collected. The registry will perform targeted follow-up to collect additional data on events and outcomes of interest as needed. Congenital malformations will be reviewed by a clinical genetics/teratology specialist on the Scientific Advisory Committee overseeing interpretation of data from the registry.

Study Size

For a range of pregnancy outcomes of interest, sample size calculations considered the number of live births needed to detect the associated effect sizes using a binomial distribution with 80% power and a 1-sided Type I (false positive) error rate of 5%. Assuming prevalence values in the reference population of 2% (major malformations) and 7.6% (preterm births), 100 exposed live births will be sufficient to detect a 4-fold increase in the risk of major congenital malformations and a 2-fold increase in the risk of pre-term births, relative to the reference-population prevalence.

Data Analysis

Demographic and baseline characteristics will be summarized with simple descriptive statistics and data listings for the evaluable population of pregnant women and live births.

Point estimates and 95% confidence intervals will be calculated using the binomial distribution for prevalence estimates of maternal death and pregnancy outcomes among pregnant women exposed to at least one dose of IV zanamivir and for birth outcomes including preterm birth, LBW, SGA and neonatal deaths among their exposed live births. Prevalence estimates for congenital malformations will consider congenital malformations identified in both live births and foetal deaths. For each prevalence estimate, both 1-sided and 2-sided 95% confidence intervals will be calculated and reported. Outcome prevalence estimates will be presented overall and stratified according to the trimester of IV zanamivir exposure.

The registry is primarily descriptive aiming to determine a signal for substantial increase in risk. Therefore, comparisons will be descriptive. Primary comparisons will be against external comparators reflecting population-based surveillance of pregnancy outcomes and literature-based disease cohorts. If it is feasible, descriptive comparisons between the registry and an appropriate internal comparator will be examined.

Milestones

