8.3.2. Outcome definitions

There are three groups of outcomes of interest:

Maternal outcomes

• Maternal death during pregnancy and up to 42 days after delivery.

Pregnancy outcomes

- Live birth defined as an infant born alive.
- Spontaneous abortion (SAB) in clinically recognized pregnancies defined as foetal death or expulsion of products of conception prior to 20 weeks' gestation, or if gestational age is unknown, weighing less than 500g.
- Stillbirths defined as a foetal death occurring at 20 weeks' gestation or greater, or if gestational age is unknown, a foetus weighing 500 g or more.
- IAB defined as voluntary interruption of pregnancy, including pregnancy termination that occurs electively, to preserve maternal health, or due to foetal abnormalities.

Birth outcomes

- Prematurity defined as an infant born at gestational age <37 weeks.
- SGA defined as an infant born with a birth weight less than the 10th centile for the corresponding gestational age.
- LBW defined as an infant whose birth weight is <2500 g.
- Neonatal death defined as death of the infant within 28 days of birth.
- Major congenital malformation (MCM) defined according to EUROCAT criteria
- EUROCAT includes all major structural malformations and chromosomal malformations. Minor anomalies are excluded (as defined in Section 3.2 of the coding guide) and cases with more than one malformation type are only counted once for the calculation of overall malformation prevalence.

Maternal and infant follow up is proposed to 3 months after birth. Longer term follow-up is not proposed as there are no pre-clinical or clinical data to suggest a signal for developmental delay. Hence, it is impossible to determine an appropriate longer term follow up period which differs substantially according to the type of developmental adverse outcome of interest. As the majority of major malformations are detected at birth, a three month follow up period is deemed adequate to maximize capture of major malformations.

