8.5. Study size

The effect sizes that are expected to be detectable were calculated. The effect size is defined as the ratio of the prevalence in exposed patients, estimated from the study, to the prevalence in the reference population. These calculations were performed using a binomial distribution, a power of 80% and a 1-sided Type 1 (false positive) error rate of 5% [Altman, 1991]. Assuming prevalence values in the reference population of 2% (MCMs) and 7.6% (preterm births), 100 exposed live births will be sufficient to detect a 4-fold increase in the risk of MCMs and a 2-fold increase in the risk of pre-term birth, relative to the reference-population prevalence. The calculations were performed using the software PASS (Version 12.0.2, copyright 1983-2013, NCSS, LCC).

Table 1Detectable effect size assuming 80% power

Sample size of live births (N)	PTB reference 7.6% ¹	LBW reference 7.0% ¹	MCM reference 2.00% ²
5	6.45	7.00	24.51
20	4.12	3.69	10.10
50	2.61	2.83	5.38
100	2.05	2.07	3.90
150	1.85	1.91	2.99

Abbreviations: LBW = low birth weight; MCM = major congenital malformations; PTB = preterm birth. ¹Prevalence from Office for National Statistics, 2015 ²Prevalence from EUROCAT, 2017

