The prevalence of preterm births, SGA and LBW will be calculated as proportions, with the number of live births as the denominator. Because MCMs are often associated with preterm birth and LBW, sensitivity analyses will be performed excluding infants with MCMs from the numerator and denominator when prevalence estimates are determined for these outcomes.

Formulas for the calculation of prevalence of the primary outcomes are presented below:

Preterm birth prevalence =	Number of preterm live births Number of live births
SGA prevalence =	Number of SGA live births Number of live births
LBW prevalence =	Number of LBW live births Number of live births
MCM prevalence =	Number of live births and foetal losses occurring at ≥ 20 weeks gestation with MCM Number of live births (all) plus number of foetal losses with MCM

Due to inconsistent ascertainment of malformations in early foetal losses these are not included in analyses. Furthermore, a conservative approach is taken to only include foetal losses ≥ 20 weeks with MCMs, rather than all foetal losses, in the denominator. This will result in an over-estimation of risk.

Because most structural defects have their origins in the first trimester of pregnancy during the period of organogenesis, analyses of MCMs will be stratified by trimester of exposure, if applicable. The second trimester will start at 14 weeks gestation and the third trimester will start at 28 weeks gestation. The prevalence of combined MCMs reported to the registry will be calculated as a proportion with the number of MCMs in live births and foetal losses as the numerator and the number of all live births plus foetal losses with a MCM as the denominator. Pregnancy losses with reported MCMs occurring at or after 20 weeks' gestation will be included in the numerator of the estimate of risk for MCMs to increase sensitivity. The prevalence of combined MCMs in exposed cases will be compared with that reported to EUROCAT AND MACDP. Only cases meeting the EUROCAT criteria will be included in the primary analysis.

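### The MCM formula omits terminations for a diagnosed malformation before 20 weeks, so its net bias is not assured to be upward

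*Protocol*

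**What the plan says.** Section 8.3.2 defines three kinds of pregnancy outcome other than live birth: spontaneous abortion (before 20 weeks), stillbirth (20 weeks or later) and IAB. Terminations for malformation belong to the third: "IAB defined as voluntary interruption of pregnancy, including pregnancy termination that occurs electively, to preserve maternal health, or due to foetal abnormalities".

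Section 8.7.1 gives the MCM formula among its primary outcomes. The numerator is live births with an MCM plus foetal losses at 20 weeks or later with an MCM. The denominator is all live births plus foetal losses with an MCM. On early losses it says: "Due to inconsistent ascertainment of malformations in early foetal losses these are not included in analyses". It then explains that unaffected losses are kept out of the denominator, calls this conservative, and adds: "This will result in an over-estimation of risk".

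The Abstract describes the same estimate in other terms: "Prevalence estimates for congenital malformations will consider congenital malformations identified in both live births and foetal deaths". Foetal losses is not defined anywhere. Spontaneous abortion and stillbirth are defined through foetal death, but IAB is not.

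Three other places bear on the point:
- 8.7.1 promises to align denominators with the external references on inclusion of foetal losses. It does not mention numerators or terminations.
- 8.7 (Prospective Registry Reports) expects most exposure to come after prenatal screening.
- 8.9 names one bias for MCMs diagnosed prenatally, and it is upward.

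**The concern.** A termination carried out because of a diagnosed malformation has a known malformation status by definition. Poor ascertainment justifies leaving out early spontaneous losses but not these cases. Severe defects found on prenatal testing are plausible candidates for termination, and the primary population admits women enrolled after such testing. The formula can therefore drop confirmed cases of the outcome it is meant to measure.

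The biases that the protocol names, in 8.7.1 and 8.9, all point upward. A reader of the final report could take an unremarkable MCM prevalence as reassuring because the method was called conservative, when the net direction is unknown. Few events are expected, so one or two omitted cases can decide whether a signal appears.

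**Working it through.** **1. The plan's own figure.** Inputs from 8.5: reference MCM prevalence 2%, N = 100, one-sided 5%, power 80%, exact binomial. P(X ≥ 5 | 100, 0.02) = 0.0508, which exceeds 0.05. P(X ≥ 6 | 100, 0.02) = 0.0155. A signal therefore needs 6 cases. Solving P(X ≥ 6 | 100, p) = 0.80 gives a ratio of 3.896, which matches the 3.90 in Table 1. At exactly 4-fold (p = 0.08) power is 82.0%, with 8 cases expected. The sample-size figures are correct.

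**2. Which terminations are counted.**

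| Event with MCM | Numerator | Denominator |
|---|---|---|
| Live birth | yes | yes |
| Stillbirth, 20 weeks or later | yes | yes |
| IAB, 20 weeks or later | unclear | unclear |
| IAB, before 20 weeks | no | no, by the explanatory text |

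The last cell rests on the explanatory text. The denominator in the displayed formula carries no 20-week limit, so the two should be worded alike.

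**3. The two biases.** Leaving unaffected losses out of the denominator multiplies the estimate by about 1 + s, where s is their ratio to live births. Dropping a share f of MCM cases multiplies it by about 1 − f. They cancel at f = s/(1 + s). The documents give no s. For an assumed s of 1% to 10%, break-even is f of about 1% to 9%.

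Illustration: 100 live births with 4 MCMs and 1 unaffected late loss.
- The protocol formula gives 4/100 = 4.00%.
- With no early termination the full count is 4/101 = 3.96%, so the protocol figure is 1% too high.
- With one early termination for MCM it is 5/102 = 4.90%, so the protocol figure is 18% too low.
- With two it is 6/103 = 5.83%, so the protocol figure is 31% too low.

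**4. Effect at the design size.** The documents give no share of MCM cases ended before 20 weeks. Let t be that share in pregnancies exposed early enough to be at risk, and q the fraction of exposures at risk. Both are assumptions. Take f = qt and the same true prevalence p = 0.08 in all exposures. The observed prevalence is p(1 − f)/(1 − pf), tested against an unchanged 2% with cutoff 6.

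| q | t | f | Apparent ratio | Power |
|---|---|---|---|---|
| any | 0 | 0 | 4.00 | 82.0% |
| 100% | 10% | 0.10 | 3.63 | 74.1% |
| 100% | 20% | 0.20 | 3.25 | 63.9% |
| 100% | 30% | 0.30 | 2.87 | 51.5% |
| 20% | 10% | 0.02 | 3.93 | 80.6% |
| 20% | 20% | 0.04 | 3.85 | 79.1% |
| 20% | 30% | 0.06 | 3.78 | 77.5% |

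**5. If the reference omits the same cases.** Apply the same formula to the 2% reference with q = 100%. The ratio stays at 4.0 to 4.1, the cutoff falls from 6 to 5, and power is 85.9%, 78.6% and 68.6% for t = 10%, 20% and 30%. The gain at 10% comes from the lower cutoff. The remaining loss comes from fewer events.

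**The case against.** Much of the opposing case stands.

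- **Scope of the over-estimation sentence.** It follows directly on the denominator choice and is right about it. A reader might infer that it is false, or that it claims a net direction for the whole formula. The text does not go that far. The early-loss exclusion is disclosed separately with its own reason.
- **Alignment with the reference.** The promise in 8.7.1 aims at like-for-like comparison, and if it is met in full the ratio is not attenuated (step 5). But it is worded for denominators only, and the protocol does not say whether the 2% includes early terminations.
- **Who is at risk.** A pregnancy first exposed at 20 weeks or later cannot end in termination before 20 weeks, and 8.7 expects mostly later exposure. That shrinks the overall effect (q = 20% rows). It also concentrates what remains in first-trimester exposure, the period in which 8.7.1 says most structural defects originate.
- **The cases are still visible.** Section 8.4 asks for MCMs in infant or foetus, a teratologist reviews all reported anomalies, and IAB prevalence is reported. This helps signal review but does not correct the prevalence estimate.
- **The registry is descriptive.** True, but the protocol itself fixes this formula and its bias statement for a primary outcome, so the point is not one merely left to the SAP.

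**Conclusion.** The point holds in a limited form. As written, the MCM estimate leaves out terminations for a diagnosed malformation before 20 weeks, for a reason that does not fit them, and it is unclear whether later ones count. Over-estimation is assured for the denominator choice only; the net bias may be upward or downward.

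A reader might infer that malformations will be substantially under-counted. The documents do not support that, because they give no share of MCM cases ended before 20 weeks. With an unaligned 2% reference and 10% to 30% of at-risk MCM cases dropped, a true 4-fold ratio appears as about 3.6 to 2.9 (power 74.1% to 51.5%) if all exposures are at risk. It appears as 3.9 to 3.8 (power 80.6% to 77.5%) if 20% are. Given the expected timing of exposure, the overall effect may be small, and the first-trimester stratum is the more exposed part.

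**What to change.** In section 8.7.1:

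1. State whether foetal losses includes IABs, and use one term and one gestational limit in the formula, the explanatory text and the Abstract.
2. Report MCM prevalence with confirmed-MCM terminations at any gestational age in both numerator and denominator, beside the current version limited to 20 weeks or later. Do this overall and for first-trimester exposure.
3. Align numerators as well as denominators, including the handling of terminations, with each EUROCAT or MACDP figure used.
4. Limit the over-estimation sentence to the denominator choice, and add that the net bias may be downward.

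Cost: one further MCM version to report. Prenatally diagnosed cases enter that version, so it should also be shown with and without women enrolled after prenatal testing, which 8.9 already plans. Little new data is needed: 8.4 already asks for MCMs in infant or foetus and records IAB. The reason for termination is not a listed variable, but a confirmed MCM in an IAB is enough. The outcome row of the table in 8.6.2.1 does not name IAB and should be brought into line.

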8.7.2. Exploratory analysis

Analyses will be stratified by trimester of exposure and other subgroups of interest, potentially including number of doses of IV zanamivir received, gestational age at enrolment and maternal age. Additional details on subgroup analyses will be described in the SAP. Comparisons may be made to external or internal cohorts, if appropriate.

Additional analyses may stratify by the variables listed below:

- Maternal characteristics (e.g., country)
- Previous pregnancy outcomes (e.g., MCMs, stillbirth)
- Pregnancy complications (e.g., preterm labour, pre-eclampsia, placental abruption)
- Influenza episode (e.g. length of hospital stay, ICU stay, oxygen requirements)
- Co-morbidities (e.g., diabetes, hypertension)
- Concomitant exposures (e.g., teratogenic medications, tobacco)
- Infant/foetus gender and multiple gestations.

8.7.3. General considerations for data analyses

This registry is primarily descriptive and designed to detect potential safety signals, rather than test hypotheses.

8.8. Quality control and Quality Assurance

Ensuring that the data obtained and delivered to GSK are of high quality will be an ongoing, multi-step process involving programming of edit checks for critical data variables in the EDC system and visual review for completeness, logic, consistency, and accuracy. eCRFs will be carefully designed to ensure data quality and integrity.

Investigators must retain all study records required by GSK and by the applicable regulations in a secure and safe facility. The investigator must consult a GSK representative before disposal of any study records and must notify the sponsor of any change in the location, disposition, or custody of the study files. Documents that individually and collectively permit evaluation of the conduct of a study and the quality of the data produced will be retained for a period of 25 years in accordance with Good Pharmacoepidemiological Practice (GPP) guidelines [International Society for Pharmacoepidemiology, 2015]. These documents should be retained for a longer period, however, if required by the applicable regulatory requirements or by an agreement with the sponsor. It is the responsibility of the sponsor to inform the investigator/institution, either directly or through the CRO, as to when these documents no longer need to be retained.

For observational studies, study records or documents may include the analyses files, syntaxes (usually stored at the site of the database), but also questionnaires.

8.9. Limitations of the research methods

The study relies on a sample of exposures identified through UKOSS/INOSS which may or may not be entirely representative of all women exposed to IV zanamivir during pregnancy. However, for a product used under very specific circumstances, this is likely one of the only and most complete methods of obtaining safety information for hospitalbased pregnancy exposures.

Because early prenatal testing is so frequent, it may be difficult to achieve adequate numbers of pure prospectively identified pregnant women if all pregnancies with prior prenatal testing are excluded from the analysis. Therefore, the primary analysis will include pregnancies enrolled prior to outcome but after prenatal testing. However, this practice could potentially bias the results by introducing more cases of MCMs identified prenatally [Honein, 1999]. The analysis will attempt to determine bias introduced by this practice by examining the data with and without these cases.

While the registry analysis will initially be limited primarily to prospective reports, some pregnancy exposures may be reported only following pregnancy outcome (retrospective cases). Each retrospective report will be carefully reviewed and an assessment of bias in terms of systematic differences in the outcomes between prospective and retrospective reports will be made. In general, retrospective reports of exposures to medication following notification of outcome are biased toward reporting of the severe and unusual cases and are not reflective of the general experience with the medication.

Given uncertainty around the circumstances when IV zanamivir will be used, it is difficult to define an appropriate comparator group. However, multiple sources of data will be used to estimate background rates of the events of interest in the general population and the feasibility of concurrently enrolling a group of pregnant women with complicated influenza untreated with IV zanamivir will also be explored.

Women may be exposed to additional anti-influenza medications prior to IV zanamivir exposure, the most common class being neuraminidase inhibitors. There is currently no evidence to suggest that exposure to NAIs is associated with adverse pregnancy outcomes so this is unlikely to modify interpretation of risk estimates for IV zanamivir [Graner, 2017].

Finally, there may be differences between countries in how antenatal care is delivered as well as perinatal outcome risks. Some feasibility landscaping work would be useful to reduce potential operational challenges and to assess the background assumptions underlying the sample size calculations.

8.9.1. Study closure/uninterpretability of results

The prevalence of exposure to IV zanamivir is likely to vary across influenza seasons influenced by factors such as the underlying pathogenicity and resistance profiles of circulating virus strains. Accordingly, an update report will be filed with the EMA each year, providing details of the number of treated patients enrolled and guidance on the likely study end date. This will be used to inform on a more realistic study end date. At present 100-150 IV zanamivir exposures are proposed to be sufficient to detect a 2-4-fold

increase in pregnancy outcomes of interest therefore detecting a signal of substantial increase in risk.

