The registry will be implemented following the granting of the marketing authorisation for IV zanamivir and before the start of the first northern hemisphere influenza season following that grant. The registry will be opened in countries within the European Union (EU), United Kingdom (UK), Norway and Iceland. At present 100-150 exposures during pregnancy to IV zanamivir are proposed to be sufficient to detect 2-4-fold increases in the risk of adverse pregnancy outcomes of interest and therefore sufficient to detect a signal for substantial increase in risk. The prevalence of exposure to IV zanamivir is likely to vary across influenza seasons influenced by factors such as the underlying pathogenicity and resistance profiles of circulating virus strains. Accordingly, an update report will be filed with the EMA each year, providing details of the number of treated patients enrolled and guidance on the likely study end date.

Amendment or update no.	Date	Section of study protocol	Amendment or update
1	23-JUN- 2020	8.4 Data source 8.7 Data Analysis, sub- section Analysis Population	Clarified that additional de-identified data, collected by HCPs to supplement the primary analysis population collected through the pregnancy study, can include the minimal dataset collected under informed consent waiver from the UKOSS/INOSS network. This will enable access to a minimal set of data on women exposed to IV zanamivir from UKOSS/INOSS but who do not consent to participate in the current study.

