8.7. Data analysis

The following approach shall be taken for outcome case management within the registry.

Prospective Registry Reports

The registry will encourage prospective registration, which is defined as registration of a pregnancy exposure prior to knowledge or perceived knowledge of the pregnancy outcome (e.g., structural defect or genetic abnormality noted on a prenatal test).

Prospective reports will be further defined as traditional prospective and pure prospective reports. Traditional prospective reports of pregnancy will include all women who enrol in the registry before the end of pregnancy (live birth, foetal loss, etc), regardless of knowledge of normal or abnormal prenatal test results. Pure prospective reports of pregnancy are a subset of traditional prospective reports and include those where (a) the enrolee did not know at the time of enrolment whether the foetus had adverse outcome such as a malformation, and (b) no prenatal testing was completed prior to enrolment. As the severity of influenza increases with trimester of pregnancy it is likely that most

exposure to IV zanamivir will occur after prenatal screening has occurred. Therefore, in primary analyses, traditional and pure prospective reports will be grouped together.

Data from HCPs that provide de-identified data on all exposed pregnancies in their network will fall into the category of prospective registry reports, as these reports provide objective data on every pregnancy exposure in the network, both positive and negative outcomes. Thus, they avoid the reporting bias inherent in retrospective reporting only after a negative outcome has been noted.

Retrospective Registry Reports

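### The 100-150 target is stated in exposures but was calculated in live births; at the lower end it falls short of 80% power for a 2-fold increase, and the 4-fold malformation figure does not carry over to first-trimester exposure

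*Protocol*

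**What the plan says.** Section 8.5 sets out the calculation: exact binomial, 80% power, one-sided 5% error, with the sample size in Table 1 counted in live births. Its text concludes that "100 exposed live births will be sufficient to detect a 4-fold increase in the risk of MCMs and a 2-fold increase" in preterm birth. For 100 live births Table 1 prints detectable ratios of 2.05 (preterm birth), 2.07 (low birth weight) and 3.90 (major congenital malformation, MCM). For 150 it prints 1.85, 1.91 and 2.99.

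Two other places restate the result in a different unit. The milestones part of the abstract says "At present 100-150 exposures during pregnancy to IV zanamivir are proposed to be sufficient to detect 2-4-fold increases" in adverse outcomes. Section 8.9.1 says "At present 100-150 IV zanamivir exposures are proposed to be sufficient to detect a 2-4-fold" increase. The study-size part of the same abstract still speaks of live births.

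The analysis rules separate the two units. Section 8.7 leaves pregnancies lost to follow-up out of the statistical analyses. Section 8.7.1 uses live births as the denominator for preterm birth, small for gestational age and low birth weight. For MCM it uses live births plus foetal losses with an MCM.

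On timing, section 8.7.1 stratifies the MCM analysis by trimester "Because most structural defects have their origins in the first trimester of pregnancy during the period of organogenesis". Section 8.7 says: "As the severity of influenza increases with trimester of pregnancy it is likely that most" exposure will come after prenatal screening.

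**The concern.** An exposure is not a live birth. Spontaneous and induced abortions, stillbirths and women lost to follow-up all count as exposures and add nothing to the denominator that Table 1 assumes. The background section itself cites higher perinatal mortality and foetal death with influenza, so these losses cannot be taken as negligible. The yearly update to the EMA is to give the number of treated patients enrolled, which is also not the count the calculation uses.

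Two further points bear on the same sentence. The text rounds 2.05 down to 2, so there is no margin at 100 even before losses. The 4-fold MCM figure spreads the risk over every live birth, while the protocol places the relevant window in the first trimester and expects most exposure later.

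What is at stake is the meaning of a null result. A report that 100 exposures showed no 2-4-fold signal would claim more sensitivity than the data had, most of all for a teratogenic effect.

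**Working it through.** **Inputs (section 8.5).** One-sided error 0.05; power 80%; reference prevalence p0 = 7.6% (preterm birth), 7.0% (low birth weight), 2% (MCM). The document gives no attrition rate and no first-trimester share, so both are assumed below over a range.

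**Formula.** Let c be the smallest count with P(X ≥ c | N, p0) ≤ 0.05. Power is P(X ≥ c | N, p1). The detectable ratio is p1/p0 where power equals 0.80.

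**Step 1: reproduce Table 1.** All 15 cells reproduce within 0.01. At N = 100 the ratios are 2.050 (c = 13), 2.071 (c = 12) and 3.896 (c = 6). At N = 150 they are 1.852, 1.909 and 2.994.

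**Step 2: power for the ratios named in the text.**

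| Live births | Preterm birth, 2-fold (15.2%) | Low birth weight, 2-fold (14%) | MCM, 4-fold (8%), all births |
|---|---|---|---|
| 100 | 77.0% | 75.9% | 82.0% |
| 150 | 88.9% | 85.6% | 96.0% |

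Exact power rises and falls as c steps up. For a 2-fold increase in preterm birth it first reaches 80% at 103 live births and stays there from 118. For low birth weight the counts are 112 and 136. For 4-fold MCM over all births they are 68 and 83.

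**Step 3: from exposures to live births.** Assume that 5% to 25% of exposures give no evaluable live birth, so that 100 exposures give 95 to 75.

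| Live births per 100 exposures (assumed) | Preterm birth, 2-fold | MCM, 4-fold, all births |
|---|---|---|
| 95 | 70.2% | 88.5% |
| 90 | 73.2% | 85.5% |
| 85 | 65.5% | 81.9% |
| 80 | 68.8% | 77.7% |
| 75 | 60.0% | 72.6% |

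The reversals between rows come from the steps in c. Between the tabulated counts, power for preterm birth peaks at 77.2% (93 live births), so no count from 75 to 95 reaches 80%. Securing 100 live births would take 100/0.95 = 105.3, so 106 exposures, up to 100/0.75 = 133.3, so 134.

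At the upper end, 150 exposures give at least 118 live births if losses stay within (150 − 118)/150 = 21%, and at least 136 if they stay within (150 − 136)/150 = 9%.

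**Step 4: MCM and first-trimester exposure.** Suppose that only first-trimester exposure carries a 4-fold risk, and let f be the first-trimester share (assumed). The overall prevalence is p = 0.08f + 0.02(1 − f).

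| f (assumed) | Overall p | Overall ratio | Power, N = 100 | Power, N = 150 |
|---|---|---|---|---|
| 10% | 2.6% | 1.3 | 5% | 10% |
| 20% | 3.2% | 1.6 | 10% | 21% |
| 30% | 3.8% | 1.9 | 18% | 34% |
| 50% | 5.0% | 2.5 | 38% | 63% |

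Analysing the first-trimester stratum alone does not restore 80%. Table 1 gives detectable ratios of 24.51, 10.10 and 5.38 for 5, 20 and 50 births. Power for a 4-fold increase is 21% with 20 such births and 57% with 50.

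**The case against.** The best defence is that Table 1 is right, that it prints 2.05 and 2.07 openly, and that a registry calling itself descriptive need not be held to three percentage points of power, some of which is discreteness (the actual error rate for preterm birth at 100 is 0.040). That stands as far as the rounding goes. It does not answer the change of unit, because it is the protocol that claims a sufficient size.

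Several stronger readings are tempting, and the document does not support them:

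- **That the target fails throughout.** It does not. At 150 live births both 2-fold figures exceed 80%, and 120 live births (20% loss from 150) still give 82.9% and 80.5%.
- **That the 4-fold MCM figure is wrong.** It fits the planned overall prevalence, which counts all live births plus foetal losses with an MCM. It also survives a fall to 85 live births (81.9%).
- **That the sentence is a closure rule.** Section 8.9.1 words it as a present proposal and leaves the end date to the annual updates. Section 8.9 itself says the sample-size assumptions should be assessed.
- **That every adverse outcome removes a live birth.** Maternal death is counted up to 42 days after delivery and need not do so. Multiple births count as several infants and offset part of the loss.
- **That the first-trimester stratum should become the primary MCM comparison.** That is a design choice. Stratification by trimester is already planned, and no first-trimester share is stated from which to judge the change.

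**Conclusion.** The point holds for the lower end of the range and for the unit. The abstract's milestones and section 8.9.1 convert a live-birth calculation into exposures with no allowance for losses. At 100 live births, power for a 2-fold increase is 77.0% (preterm birth) and 75.9% (low birth weight). At 100 exposures it is lower, about 60-73% for preterm birth at the tabulated counts from 75 to 95 live births. That last figure rests on the assumed attrition and ignores the partial offset from multiple births. The upper end is adequate if losses stay below about 21% (preterm birth) or 9% (low birth weight).

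For MCM the point is a limit on interpretation. The 4-fold figure is met over all live births and says little about first-trimester exposure, where a 4-fold effect diluted over 100 live births has 5-38% power at assumed shares of 10-50%. That first-trimester exposure will be the minority is the natural reading of section 8.7, but no share is given.

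The sentence in section 8.9.1 also speaks of outcomes of interest in general, although section 8.5 calculates only preterm birth, low birth weight and MCM.

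**What to change.** - In the abstract's milestones and section 8.9.1, state the target in evaluable live births and give the attrition assumed in turning it into exposures.
- In section 8.5 and the abstract, give the detectable ratio at 100 live births as 2.05 (preterm birth) and 2.07 (low birth weight). If a true 2-fold is wanted at 80% power, cite about 118 and 136 live births.
- Say that the 4-fold MCM figure applies to births exposed in any trimester, and point to the Table 1 ratio for the number of first-trimester-exposed births.
- Limit the 2-4-fold sentence to preterm birth, low birth weight and MCM.
- In each annual update, report evaluable live births, overall and first-trimester-exposed, beside the number of treated patients enrolled.

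The cost is wording in three places and one added count in the annual report. No additional patients and no change of primary comparison are needed. The stated figures become slightly less favourable.
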